8 STUDY DRUG TREATMENT

8.1 Description of Products

Study drug treatment will include once daily application of SB206 10.3% or Vehicle (placebo) gel. Each dose will consist of berdazimer gel or vehicle gel that will need to be mixed with

hydrogel on a supplied dosing guide, and then immediately applied by the subject or caregiver to the affected designated area(s).

All study drug treatments will be manufactured and provided by the sponsor. The study treatments and their attributes are described in [Table 7](#).

Table 7 Study Drug

[figure not shown]
	SB206 10.3%	Vehicle gel
Study Drug Components	Berdazimer gel 22.7% and buffered hydrogel Mixed immediately prior to application	Vehicle gel and buffered hydrogel Mixed immediately prior to application
Name of Active Ingredient	Berdazimer Sodium	None
Packaging	One kit will include 3 x 14g aluminum tubes of berdazimer gel and 3 x 14g aluminum tubes of hydrogel	One kit will include 3 x 14g aluminum tubes of vehicle gel and 3 x 14g aluminum tubes of hydrogel
Storage Requirements	Refrigerated, horizontal 2-8°C until dispensed	Refrigerated, horizontal 2-8°C until dispensed
Appearance Post-Mixing	Opaque white gel	Opaque white gel
Dosing Schedule	QD	QD
Route of Administration	Topical Application	Topical Application

Note that description of the concentration of SB products used nominal numbers based on percent berdazimer sodium historically. Novan has updated the naming convention to use percent berdazimer. Therefore, SB206 12% (nominal berdazimer sodium) is the same admixture formulation as SB206 10.3% (berdazimer). In this protocol, the nominal berdazimer sodium numbers remain in historical studies.

8.1.1 Formulation, Storage, Preparation, and Handling

SB206 is a two-component drug product formulation intended for topical administration. The drug product is comprised of an active gel component containing the berdazimer sodium drug substance, and a buffered hydrogel (aqueous) component that when mixed releases nitric oxide. Berdazimer sodium is silsesquioxanes, 3-(2-hydroxy-1-methyl-2-nitrosohydrazinyl)propyl 3-(methylamino)propyl, polymers with silicic acid (H₄SiO₄) tetra-Et ester, hydroxy-terminated, sodium salts.

Figure 4 Structure of Berdazimer Sodium (active ingredient in SB206)

8.2 Dosing and Administration

During the double-blind treatment period, study drug will be assigned using an IWRS. Approximately 850 subjects, 6 months of age and older, with a minimum of 3 and a maximum of 70 lesions at Baseline will be randomized. A drug kit consisting of 6 tubes of assigned study drug sufficient for 4 weeks of dosing will be dispensed to the subject at the Baseline Day 1 visit. A second kit will be dispensed at Week 4, and a third kit will be dispensed at Week 8. Three of the tubes will contain berdazimer gel or vehicle gel and 3 of the tubes will contain buffered hydrogel. When the gel and hydrogel are mixed together, the components form a gel that will be applied to the lesions. If a subject's lesions have been confirmed by an investigator as completely cleared at Weeks 4 or 8, a new kit should still be dispensed so that the subject can resume once daily treatment in the event of recurrence or new lesions prior to the next scheduled visit.

The first study drug dose will occur on Baseline Day 1, with application by the subject or caregiver following training by the site. Subsequent applications of study drug occur at home or on-site at the clinic visits at Week 2, Week 4 (if the visit is performed in clinic), Week 8, and Week 12. Subjects will return their kit to each clinic visit for weight and retraining purposes; at Week 2 only, the kit will be re-dispensed to the subject.

The following is a summary of the subject's/caregiver's role in treatment of lesions:

- Continuous daily treatment of treatable lesions to Week 4 at a minimum
- Continued treatment of treatable lesions after Week 4 unless otherwise instructed by the Investigator
- Self-initiated treatment of new or recurrent lesions
- Documentation of daily dose application in subject diary

Withdrawal and discontinuation are covered in Section 6.8.

8.3 Treatment Allocation

Subjects will be randomly assigned in a 1:1 fashion to either SB206 10.3% or Vehicle gel.

8.4 Randomization Strategy and Procedure

The randomization schedule will be computer generated using a permuted block algorithm and will randomly allocate IP to randomization numbers. As subjects qualify to be randomized into the study, a randomization number will be assigned through a central IWRS. At randomization, subjects will be stratified by investigator type (dermatologist vs. other), the subject's BOTE score at Baseline (no inflammation (BOTE = 0) vs. mild/moderate/severe inflammation (BOTE \geq 1) and number of randomized subjects per household (1 subject per household vs. 2 subjects per household). Subjects will be stratified to 5 strata first by subjects per household. Subjects from 1 subject households will be stratified by investigator type and baseline BOTE score. Subjects from 2 subject households will not be further stratified with respect to investigator type and baseline BOTE score because the overall sample size that is expected for the stratum for households with two subjects is not large enough to support further stratification. Approximately 850 subjects, 6 months of age and older, with a minimum of 3 and a maximum of 70 lesions at Baseline will be randomized.

8.5 Extent and Maintenance of Blinding

All subjects, investigators, and study personnel involved in the conduct of the study will be blinded to treatment assignment, with the exception of a specified unblinded statistician who will generate and have access to the randomization code. The unblinded study personnel will not otherwise participate in study procedures or data analysis prior to unblinding of the study data to all study related personnel.

Study personnel will endeavor to safeguard the integrity of the study blind to minimize bias in the conduct of the study.

8.5.1 Unblinding Procedures

8.5.1.1 Planned Unblinding

Individual treatment unblinding is discouraged since knowledge of the treatment assignment will not materially change the planned management of a medical emergency. Unblinding should be discussed in advance with the medical monitor if possible. Study personnel will utilize the IWRS for emergency unblinding. If the investigator is not able to discuss treatment unblinding in advance, then he or she must notify the CRO medical monitor as soon as possible about the unblinding incident without revealing the subject's treatment assignment. The investigator or designee must record the date and reason for study discontinuation on the appropriate eCRF for

that subject. In all cases that are not emergencies, the investigator must discuss the event with the medical monitor prior to unblinding the subject's treatment assignment.

If treatment assignment is unblinded for an individual subject, study personnel will be notified of that subject's treatment assignment without unblinding the treatment assignments for the remaining subjects in the study. Thus, the overall study blind will not be compromised. If a subject's treatment assignment is unblinded, he or she may or may not be asked to withdraw from the study. The investigator will make this decision after consultation with the medical monitor.

Of note, all available unblinded safety data will be provided to the DSMB to review after approximately 200 subjects are randomized. Personnel who are not otherwise involved in the study will prepare the unblinded data and summary tables for this analysis.

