This is a phase 3 multi-center, randomized, double-blind, vehicle-controlled, parallel group study to be conducted in approximately 850 subjects with MC. After obtaining informed consent/assent, subjects who satisfy entry criteria will be randomized 1:1 (active:vehicle) using an interactive web response system (IWRS). Subjects receiving current treatment for MC at the time of the Screening Visit will enter a wash out period of up to 14 days prior to randomization. In the event no wash out period is required, Screening and Baseline visit activities may be combined into a single in-clinic visit. At randomization, subjects will be stratified by investigator type (dermatologist vs. other), the subject's BOTE score at Baseline (no inflammation (BOTE = 0) vs. mild/moderate/severe inflammation (BOTE \geq 1) and number of randomized subjects per household (1 subject per household vs. 2 subjects per household). Subjects will be stratified to 5 strata first by subjects per household. Subjects from 1 subject households will be stratified by investigator type and baseline BOTE score. Subjects from 2 subject households will not be further stratified with respect to investigator type and baseline BOTE score because the overall sample size that is expected for the stratum for households with two subjects is not large enough to support further stratification.

A maximum of two subjects from the same household may be randomized to the study. They must be randomized on the same day and both must individually meet all inclusion/no exclusion criteria. For subjects in the same household, Screening can occur on different days; however, the Baseline visit must occur on the same day. Households randomizing two subjects will receive the same treatment assignment for both subjects.

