Subjects or their caregivers will apply SB206 10.3% or Vehicle Gel once daily for a minimum of 4 weeks and shall continue unless otherwise instructed by the investigator up to 12 weeks to all lesions identified at Baseline and new treatable lesions that arise during the course of the study. Subjects or their caregivers will continue to treat the area until the next scheduled visit even if the lesion(s) clear. At each in-clinic and remote visit, the investigator will count and record the number of active (raised, treatable) molluscum lesions per body area. Complete clearance should be confirmed by an in-clinic lesion count before treatment is discontinued. If the investigator determines all lesions are cleared at a visit, the investigator may instruct the subject to stop treatment. If treatment is stopped due to clearance, subjects will continue regularly scheduled visits through Week 12/ET and all procedures outside of study drug activities should be continued. If lesions recur or new lesions occur between visits after being stopped due to clearance, the subject or caregiver should re-initiate treatment to the recurring and new lesions. A new kit should be dispensed at Weeks 4 and 8 regardless of lesion count so that treatment can be restarted if lesions are observed between visits. An unscheduled visit is not required for the subject/caregiver to resume treatment. No study treatment is planned to be dispensed after the Week 12 visit.

Remote visits may be performed at Week 4 using remote technology. During the Baseline visit, the subject/caregiver will be instructed on the technology to be used for remote visits. After the initial molluscum lesion count is completed, it will be repeated by the same assessor and the subject/caregiver using the subject/caregiver's electronic device that will be utilized to capture photographs for remote visits. This will provide the subject/caregiver an opportunity to practice with the technology and will allow for the assessor to understand lesion appearance in person compared to through the technology platform.

Subjects will be contacted via phone on Day 2 to collect subject information on early dose reactions. At Weeks 16 and 20, subjects will be contacted via phone to capture information regarding MC recurrence and adverse events (AEs); at Week 24, the subject will be seen at the site for a final study visit to assess scarring, keloid, and MC recurrence.

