## 9.5 Protocol Deviations

Significant protocol deviations that could potentially affect the efficacy or safety conclusions of the study will be identified prior to database lock and unblinding of individual subject treatment information. Significant protocol deviations may include, but are not limited to:

- Randomly assigned subjects who did not satisfy selected inclusion and exclusion criteria
- Randomly assigned subjects who developed withdrawal criteria during the study but were not withdrawn
- Subjects who were randomized incorrectly including subjects of the same household who are randomized to different treatments
- Subjects who received the wrong treatment
- Subjects where the subject/site staff were improperly unblinded
- Week 12 Lesion Count not performed
- Subjects who received an excluded concomitant treatment.

The decision on the criteria for whether a subject is excluded from the PP Population will be made during the data review meeting prior to unblinding and database lock. Reasons for exclusion of a subject from the analysis will be listed.

A listing of all protocol deviations including the deviation designation (major or minor and significant or not), category, and indication of whether the deviation led to an exclusion of a subject from the PP Population will be presented in a data listing. Additionally, a listing of missed visits due to COVID-19 will be presented.

Major and significant protocol deviations will be summarized by deviation category and treatment group.

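### Protocol 8.5.1.1 says unblinding one subject leaves all the others blinded; this is false for two-subject households, which share one treatment, and the rule does not keep the assignment from lesion counters

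*Protocol*

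**What the plan says.** Three parts of the plan bear on this.

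**Allocation.** Protocol 4.1 allows pairs: "A maximum of two subjects from the same household may be randomized to the study". It then fixes their treatment: "Households randomizing two subjects will receive the same treatment assignment for both subjects". SAP Section 4 repeats the rule.

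**Code break.** Protocol 8.5 sets the general rule: "All subjects, investigators, and study personnel involved in the conduct of the study will be blinded to treatment assignment". Protocol 8.5.1.1 is the procedure for exceptions. Study personnel break the code through the IWRS. An investigator who could not consult beforehand informs the CRO medical monitor "without revealing the subject's treatment assignment". Once a subject is unblinded, "study personnel will be notified of that subject's treatment assignment without unblinding the treatment assignments for the remaining subjects in the study". The section concludes: "Thus, the overall study blind will not be compromised". The unblinded subject may stay in the study. Household pairs are not mentioned.

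**Recording and analysis.** Protocol 8.5.1.2 requires documentation of unplanned or unintentional unblinding. SAP 9.5 gives examples of significant deviations, one of which is "Subjects where the subject/site staff were improperly unblinded". That list is stated to be non-exhaustive, and Per-Protocol exclusions are decided at a data review meeting before unblinding and database lock.

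On who assesses the endpoint, Protocol 4.1 says that at each in-clinic and remote visit "the investigator will count and record the number of active (raised, treatable) molluscum lesions per body area". Sections 6.6 and 7.1.1 want the same evaluator at Baseline and Week 12. Section 7.1.1 allows a different trained evaluator when that cannot be arranged.

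**The concern.** The primary endpoint is a lesion count of zero, judged by an assessor on the skin. BOTE and LSR scores and AE causality are also matters of judgement. An assessor who knows the arm can be influenced by it.

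The plan puts both members of a household in the same arm on purpose. One consequence is that the two blinds stand or fall together, and the code-break section does not recognise this. The co-enrolled member stays in the study and supplies a Week 12 count, and nothing marks that count as made with the arm known. The same holds for the target subject if he or she stays. Nothing in 8.5.1.1 keeps the assignment from the usual lesion counter or asks for another evaluator afterwards.

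Counts made this way enter the primary ITT analysis. They can also remain in the Per-Protocol analysis unless someone at the review meeting thinks to ask. The SAP's one-subject-per-household sensitivity analysis does not address it, because it selects by baseline lesion count and then age and so may keep the exposed member.

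**Working it through.** **Step 1: the logic.** No figure in the plan is contested, so the first check sets the texts side by side.

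- Premise A (Protocol 4.1, SAP 4): in a two-subject household, the arm of member 1 equals the arm of member 2.
- Premise B (Protocol 8.5.1.1): the arm of member 1 is disclosed to study personnel.
- Consequence: anyone who is told, and who knows the two are enrolled together, knows the arm of member 2. The site knows this, because Protocol 4.1 requires both Baseline visits on the same day and household size is a stratification factor.
- Limit: a household has at most two subjects, so a code break exposes at most one further subject. Subjects in other households stay blinded.

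**Step 2: the lesion counter.** The investigator counts lesions (4.1), assesses causality (9.2.2) and handles code breaks (8.5.1.1). The personnel to be notified are not defined so as to leave assessors out. Exposure of the counter is therefore possible, but the plan does not say it will happen.

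**Step 3: what is recorded.**

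| Event | Protocol 8.5.1.2 | SAP 9.5 examples |
|---|---|---|
| Improper or unintentional unblinding | Yes | Improper unblinding named |
| Permitted code break, target subject | Not named | Not named |
| Co-enrolled member exposed by it | Not named; arguably unintentional | Not named |

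**Step 4: size.** The plan gives neither the number of code breaks nor the share of subjects in two-subject households. It says only that the stratum is too small to subdivide. Both are therefore assumptions.

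- Proxy for code breaks: serious TEAEs in Protocol Table 2, (0 + 0 + 1 + 1) / (116 + 235 + 117 + 237) = 2/705 = 0.28%. Applied to 850 subjects: 850 × 2/705 = 2.4.
- Share s of subjects in two-subject households: assumed 5% to 30%, about 42 to 255 of 850.
- Expected extra subjects exposed = code breaks × s, if code breaks fall at random on different households: 2.4 × 0.05 = 0.12 to 2.4 × 0.30 = 0.72.
- If there were 5 code breaks (also an assumption): 5 × 0.05 = 0.25 to 5 × 0.30 = 1.5.

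For scale, one changed response moves an arm of 425 by 1/425 = 0.24 percentage points, and a whole pair moves it by 2/425 = 0.47. The planned difference is 9.5 points.

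The proxy is rough in both directions. Table 2 runs through Week 24, while only unblinding before the Week 12 count can affect the endpoint. Protocol 8.5.1.1 discourages code breaks, and Protocol 2.1.4.2 reports no treatment-related serious events. On the other hand, non-emergency unblinding is allowed after discussion with the medical monitor, so the proxy is not a ceiling.

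**The case against.** The strongest reply is that this is a rare event, the overall blind is safe and the plan already has room to deal with it. Much of that stands, and it rules out several stronger readings that a reader might infer.

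- **That 8.5.1.1 contradicts its own preceding paragraph.** It does not. The instruction to inform the medical monitor "without revealing the subject's treatment assignment" keeps the CRO monitor blinded. It does not restrict what the site team that breaks the code may learn. The two sentences concern different recipients.
- **That 8.5.1.1 contradicts 8.5.** It does not. Section 8.5 is the general rule and 8.5.1 is the procedure for exceptions; any code break departs from the general rule.
- **That the overall blind is lost.** This is not shown. One more exposed subject among about 850 does not undo the study blind. What fails is the clause about the remaining subjects, and only for pairs.
- **That the SAP prevents these subjects from being reviewed.** It does not. The 9.5 list is open and the review meeting may consider them. Exposure of the other household member can also be read as unintentional unblinding under 8.5.1.2, which would then require documentation.

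What remains after these concessions is that 8.5.1.1 is untrue for pairs, its notification rule has no exclusion for assessors, and nothing expressly prompts anyone to record or review the second member.

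It can also be said that limiting disclosure does not help when the person who breaks the code is the usual counter. That is correct, and the fix has to deal with that case separately.

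**Conclusion.** The point holds in a narrow form. As written, 8.5.1.1 is wrong for every two-subject household, by the plan's own allocation rule and with no outside assumption. Its notification rule leaves the lesion counter's blind unprotected, and neither 8.5.1.2 nor SAP 9.5 expressly captures a permitted code break or the co-enrolled member.

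The expected numerical effect is very small: 0.12 to 0.72 extra subjects. That rests on serious TEAEs as a proxy for code breaks, on random occurrence, and on an assumed 5% to 30% household share that the plan does not give. It should not be read as a threat to the primary conclusion. It is a minor correction, worth making because the statement is untrue and costs little to repair.

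**What to change.** 1. **Protocol 8.5.1.1, disclosure.** Limit disclosure of the assignment to those who need it for the emergency. Do not pass it to evaluators of lesion counts, BOTE or LSR who took no part in the code break. Where the person who broke the code is the usual counter, use another already trained evaluator for later counts if one is available; 7.1.1 already permits a substitute.
2. **Protocol 8.5.1.1, pairs.** State that a code break in a two-subject household counts as unblinding both members, and record both with the date.
3. **SAP 9.5.** Add to the listed deviations any unblinding before the Week 12 count, whether permitted or not, for the subject and the co-enrolled household member, for consideration at the Per-Protocol review.

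The ITT analysis is unchanged. The cost is protocol and SAP wording and a paired record of the code break. The downside is that a very few more subjects may leave the Per-Protocol set. A change of evaluator after a code break also gives up some continuity of counting for those subjects.

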8.5.1.2 Unplanned or Unintentional Unblinding

All instances of unplanned or unintentional unblinding will be documented.

8.6 Assessment and Verification of Compliance

Subjects will be provided a diary to record doses taken on a daily basis. The diary will contain a reminder for subjects to not administer their dose the day of each visit. Review of subject compliance with the diary completion and dosing will be conducted at each visit. Subject compliance will be based on calculation from the missed doses recorded from the subject diary and from additional information noted in the source (e.g. investigator instructed interrupted or modified doses).

8.7 Prior and Concomitant Therapies

At Screening, prior MC medications/therapies taken within 6 months of Screening will be recorded. Subjects receiving medicinal treatment or other therapy for MC as defined in the study Exclusion Criterion #4, 5, or 6 at the time of the Screening Visit may enter a washout period of up to 14 days prior to the Baseline visit. Subjects receiving or that have received an investigational drug/device within 14 days or 5 half-lives (whichever is longer) prior to Baseline as described in Exclusion Criterion #13 may enter a washout period of up to 14 days prior to the Baseline visit (Section 5.2).

Initiation of new medications and changes to ongoing medications will be reviewed and documented at each study visit from Screening through Week 24, as well as at Unscheduled Visits. Any medication/therapy used by the subject following first application of study product will be considered a concomitant medication (e.g., aspirin, acetaminophen, birth control pills, vitamins, etc.). Every attempt should be made to keep concomitant medication/therapy dosing constant during the study. Any change to concomitant medications/therapies should be noted on the subject's study record and in the study database. When applicable, an AE should be completed for any subject starting a concomitant medication/therapy after enrollment into the study.

Clinically significant LSRs (e.g., those that interfere with a subject's normal daily activities) that are reported as adverse events and/or subject reported intolerability (i.e. itching, pain) may result in an investigator directed temporary treatment hold (drug holiday), and topical corticosteroids may be used to treat LSRs for up to 2 weeks. The subject may re-initiate study drug treatment prior to the next scheduled visit. Upon re-initiation (challenge) of study drug treatment, if a subject develops worsening LSRs, allergic contact dermatitis may be suspected. In the event of suspected allergic contact dermatitis, the investigator will discontinue the subject from study drug treatment and treat the area(s) with corticosteroids for up to 2 weeks. If the subject provides consent/assent, the investigator will consult the CRO medical monitor to implement the process for patch testing

